Human Platelet Extract
(HPETM) is an effective topical cosmetic product for anti-aging and facial rejuvenation.

NCT05457491

4/19/2022

General Study Information

Effective: 9/20/2017

Principal Investigator: [name]., Ph.D.

Study Title: Novel Antiaging Regenerative Skin Care Regimen Containing Human Platelet Extract (HPE)

Protocol version number and date: Version 06 – April 19, 2022

Research Question and Aims

Hypothesis: Human Platelet Extract (HPETM) is an effective topical cosmetic product for anti-aging and facial rejuvenation.

Aims, purpose, or objectives:

The objective of this cosmetic study is to evaluate the role of HPE on aging skin appearance.

To assess the effect of HPE on fine lines/wrinkles, skin tone/texture, erythema, and pigmentation.

To compare the effect of HPE to market-competitor topical antioxidant (SkinceuticalsTM CE Ferulic).

Background (Include relevant experience, gaps in current knowledge, preliminary data, etc.):

Skin aging is caused by free radical destruction of proteins, lipids, deoxyribonucleic acid (DNA), ribonucleic acid (RNA), organelles, and other vital structures. Under normal conditions, free radical damage is repaired by antioxidants, but these unfortunately decline with age, increasing the likelihood of continuous damage. Oxidative stress occurs when there is a loss of balance between free radical damage and cellular antioxidant self-repair [1]. This balance favors oxidation as small, nontoxic amounts of reactive oxidative species are required for cellular communication, immune system function, and control of the cell life cycle, which leads to beneficial cellular adaptation and balance. The skin also receives damage from free radicals generated by external factors, such as air pollutants, smoking, and changes in humidity and temperature [2]. These extrinsic causes of skin aging become more pronounced on sun-exposed areas such as the face and dorsal hands.

The visibility of the skin represents a unique organ system that facilitates inspection following application of topical formulations. The scientific literature is replete with evidence supporting the beneficial effects of many minerals, vitamins, antioxidants, anti-inflammatories, and growth factors in terms of skin hydration and firmness. Here, we describe and evaluate HPE formulation designed to improve skin appearance.

Non-FDA Approved Drug/Products

This study is testing non-FDA approved cosmetic products:

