Ingredients: Purified Water, Glycerin, Pentylene Glycol, Panthenol, Human Platelet Extract, Polyacrylate Crosspolymer-6, Hyaluronic Acid, Caprylyl Glycol, 1,2-Hexanediol, Arginine, Hydrolyzed Gelatin, Silanetriol

Warning: Use only as directed. For external use on the skin only. Do not apply to broken skin. Avoid direct contact with eyes. If contact occurs, rinse thoroughly with water. Discontinue use if skin irritation develops.

15 ml e / 0.5 fl.oz.

CLINICALLY STUDIED*

Based on an 8-weekanti-aging clinical study with 35 participants, visible results are shown after using the Revitalizing Essence.

*performed under IRB approval by a third-party product clinical testing lab

Effective: 9/20/2017

A patented daytime vitamin C serum that delivers advanced environmental protection and improves the appearance of fine lines and wrinkles, loss of firmness, and brightens skin's complexion. Now clinically proven to reduce combined oxidative damage from free radicals generated by UV, Ozone, and Diesel Exhaust by up to 41%. U.S. Patent No. 7,179,841.

SKIN TYPES: Dry, Normal, Combination, Sensitive

SKIN CONCERN: Sensitized, Dehydrated, Discoloration, Aging

FEATURES:

C E Ferulic features a synergistic antioxidant combination of 15% pure vitamin C (L-ascorbic acid), 1% vitamin E (alpha tocopherol), and 0.5% ferulic acid to enhance protection against environmental damage caused by free radicals that can contribute to atmospheric aging. C E Ferulic is now proven to reduce combined oxidative damage generated by UVA/UVB rays, ozone pollution, and diesel engine exhaust by up to 41%. In addition to antioxidant protective benefits, C E Ferulic improves signs of aging and photodamage, the appearance of lines and wrinkles, and the loss of firmness, while brightening skin's complexion.

BENEFITS:

- · Provides advanced environmental protection by neutralizing damaging free radicals
- · Visible anti-aging benefits, such as the improvement of the appearance of lines and wrinkles, loss of firmness, and brightens skin's complexion
- Neutralizes free radicals on the upper layer of the skin to help prevent the impact of ozone damage to skin
- Once absorbed, this vitamin C serum remains effective for a minimum of 72 hours
- Paraben-free and ideal for normal, dry, and sensitive skin types
- Tested suitable for use post-laser, always consult with a physician for individual post-procedure care

• 15% L-ascorbic acid

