 The study involves data that exist at the time of IRB submission and data that will be generated after IRB submission. Include this activity in the Methods section. Examples The study plans to conduct a retrospective chart review and ask subjects to complete a questionnaire. The study plans to include subjects previously diagnosed with a specific disease and add newly diagnosed subjects in the future. 					
The study will use data that have been collected under another IRB protocol. Include in the Methods section and enter the IRB number from which the research material will be obtained. When appropriate, note when subjects have provided consent for future use of their data and/or specimens as described in this protocol.					
Enter one IRB number per line, add more lines as needed					
Data Specimens Data & Specimens					
☐ Data ☐ Specimens ☐ Data & Specimens					
☐ Data ☐ Specimens ☐ Data & Specimens					
Data Analysis					

Power analyses may not be appropriate if this is a feasibility or pilot study, but end-point analysis plans are always appropriate even if only exploratory. Provide all information requested below, or provide justification if not including all of the information.

Data Analysis Plan:

All continuous data will be analyzed using independent 2-group t tests and reported as means \pm standard deviations. Categorical data will be compared between the 2 groups using chi-square tests and reported as counts and percentages. Nonparametric equivalents Wilcoxon rank-sum and Fisher exact tests will be used as needed for nonnormal distributions and low variable numbers, respectively. Treatment effects on outcomes will be compared between baseline versus HPE and HPE versus market competitor group with a significance level of p < 0.05.

Endpoints

Primary:

Evaluation of the tolerability of the study product.

- a. Nature, incidence, and severity of adverse events (AEs)
 - 1) Defined as any untoward or undesirable medical occurrence in the form of signs, symptoms, abnormal findings, or diseases that emerge or worsen relative to baseline (i.e., if present upon study entry) during the study regardless of causal relationship.
 - 2) Assessment
 - i. Incidence and severity of AEs (mild, moderate, severe)
 - ii. Relationship of AEs to study product (probable, possible, unlikely, unrelated)
 - 1. If possibly or probably related to the study product, determine whether related to the product itself or procedures pertaining to delivery of the study product.

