 - iii. Incidence of serious adverse events (SAEs) defined as AEs that result in death, life threatening adverse experiences, hospitalization, new or prolonged disability/incapacity, persistent or significant congenital defect/anomaly, or other events that in the opinion of the PI may have adversely affected the rights, safety, or welfare of the subjects or others, or substantially compromised the research data.
 - 3) Methods
 - i. Spontaneous subject reports
 - ii. Subject interview by study personnel
 - iii. Clinical examination during face-to-face clinic follow-ups
 - 4) Timing
 - i. Baseline
 - ii. 6-week post-treatment (acute)
 - iii. 12, 26- and 52-weeks post-treatment (delayed)

Change in photoaging scores from Baseline at 6,12, 26- and 52-weeks.

a. Canfield VISIA CR Gen 5 with 3DPrimos will be used to evaluate qualitatively and quantitatively skin profile changes (color evenness and roughness measurements), and to assess wrinkle count, depth, and volume by a full-aligned facial and bilateral dorsal hands images.

Information about Canfield VISIA CR is a high-resolution clinical imaging system (21 Megapixel resolution 45MP Canon EOS R5) which uses LED lighting. No radiation-based exposure. It captures high-resolution

photographic images. More information on prior model (without 3D Primos): https://www.canfieldsci.com/common/docs/products/1/brochures/VISIACRBrochure.pdf

Secondary:

- 1) Dermatopathologic evaluation of the skin
 - a) Skin microbiome: To define skin facial microbial clades, a standard swab and tape stripping method will be used on all interested subjects. Both methods are minimally invasive and can yield optimal results. All subjects will be offered skin microbiome analysis unless they did not meet criteria (i.e., washed face 3-hours prior to clinical visit, which would shift the skin microbiome; or prior allergy to adhesives) or unless they decline
 - i) Skin microbiome: Skin swab collection (n=80)
 Skin bacteria will be collected by the swabbing method as described in previous studies [4]. In brief, the left and right malar cheeks will be gently swabbed with a single dry cotton swab in a Z-stroke manner [5]. For skin microbiome, the swab head will be stored in a sterile 1.5-mL centrifugation tube at -80°C until ready for analysis.
 - ii) Skin microbiome: Tape-stripping collection (n=80)

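### The primary photoaging endpoint is analysed with independent-sample tests on within-subject data, which costs power, and no measure, visit or contrast is named as deciding the hypothesis

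*Combined protocol and SAP*

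**What the plan says.** **Test and level.** The Data Analysis Plan states: "All continuous data will be analyzed using independent 2-group t tests". The fallback for non-normal data is the Wilcoxon rank-sum test, and categorical data go to chi-square or Fisher tests; all of these assume independent groups. Treatment effects are compared as "baseline versus HPE and HPE versus market competitor group with a significance level of p < 0.05". Sidedness is not stated.

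**Endpoint.** Under Endpoints, Primary, after tolerability, the protocol lists "Change in photoaging scores from Baseline at 6,12, 26- and 52-weeks". No photoaging score is defined. The imaging is to give colour evenness and roughness, and "to assess wrinkle count, depth, and volume by a full-aligned facial and bilateral dorsal hands images".

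**Design.** Study Design and Methods and Study procedures have all 80 main-study subjects apply HPE to the face, HPE to the right hand and the competitor to the left hand. Figure 1 lists the left hand at weeks 0, 6 and 12. Follow-up at weeks 26 and 52 is by subject preference and concerns face and decolletage.

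**Claim.** The hypothesis is that HPE "is an effective topical cosmetic product for anti-aging and facial rejuvenation". The aims are "To assess the effect of HPE on fine lines/wrinkles, skin tone/texture, erythema, and pigmentation" and "To compare the effect of HPE to market-competitor topical antioxidant".

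**The concern.** There are two separate faults.

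1. **Wrong test.** Each comparison sets a subject against the same subject, at an earlier visit or on the other hand. An independent-sample test ignores that pairing. If the paired values are positively correlated, as repeated images of one person would be expected to be, the standard error is too large and real effects are missed. No paired or repeated-measures method appears anywhere in the document.

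2. **No decision rule.** The hypothesis is a yes/no efficacy claim, but the plan does not say which measure, site, visit or contrast settles it, what result would count as failure, or how multiple results are handled. A single significant cell could be cited in support.

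The faults pull in opposite directions: the first makes each test conservative and the second multiplies the chances of a false positive. The net error rate therefore depends on correlations that the document does not give.

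**Working it through.** **Plan figure to reproduce.** There is none. Accrual is 80 + 50 = 130, with no power, effect size, SD or correlation stated.

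**Inputs.** From the document: n = 80 subjects; level 0.05 per comparison; five named measures; four post-baseline visits for the face; weeks 6 and 12 for the hands. Assumed: two-sided tests, equal SDs, a within-subject correlation r common to all tests, and a stated correlation between tests.

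**Step 1: effect of ignoring the pairing.** The true variance of a mean difference is 2σ²(1−r)/n; the planned test uses 2σ²/n. It therefore rejects only when the correctly scaled statistic exceeds 1.96/√(1−r). Take the effect at which a paired test has 80% power, that is 1.96 + 0.842 = 2.802 paired standard errors (normal approximation).

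- Power of the planned test = Φ(2.802 − 1.96/√(1−r)).
- True per-test level = 2[1 − Φ(1.96/√(1−r))].

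| r | 1.96/√(1−r) | Power (paired = 80%) | Per-test level |
|---|---|---|---|
| 0.3 | 2.343 | Φ(0.459) = 68% | 0.0191 |
| 0.5 | 2.772 | Φ(0.030) = 51% | 0.0056 |
| 0.7 | 3.578 | Φ(−0.777) = 22% | 0.00035 |

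**Step 2: number of tests (an assumption).** With one photoaging score: face against baseline at 4 visits plus hand against hand at 2 visits = 6, or 8 if the right hand is also tested against baseline at weeks 6 and 12. With each of the five named measures tested: 5 × 6 = 30 or 5 × 8 = 40.

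**Step 3: family-wise error under the plan as written.** For k independent tests at the per-test level a from Step 1, it is 1 − (1 − a)^k.

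| r | 8 tests | 40 tests |
|---|---|---|
| 0.3 | 14% | 54% |
| 0.5 | 4% | 20% |
| 0.7 | 0.3% | 1.4% |

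With 40 tests the error reaches 5% at r of about 0.63 and is lower above that. A common r is a simplification. If visits correlate at 0.8 but the two hands' changes only at 0.3, the ten hand-against-hand tests alone give 1 − (1 − 0.0191)^10 = 18%, and the others add almost nothing.

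**Step 4: family-wise error if the tests are paired and nothing else changes.**

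- Independent tests: 1 − 0.95^8 = 34%; 1 − 0.95^40 = 87%.
- Between-test correlation 0.5 (equicorrelated normals, numerical integration): 25% for 8 tests, 57% for 40.

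**Step 5: price of a decision rule.** Detectable standardised difference for a paired t test with 80 pairs and 80% power: 0.317 at level 0.05; 0.390 at 0.05/5 = 0.01 (strictest Holm step over five measures); 0.418 at 0.025/5 = 0.005 (if alpha is also split between the two contrasts).

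**The case against.** **The written test is conservative, so there is no type I error problem.** Largely fair. A reader might infer that the plan as written carries an error rate of 80% or more, or that independent t tests inflate false positives. The document supports neither: those rates arise only for paired tests without a decision rule, which nobody has planned, and with positive correlation the independent test errs the other way. What remains is that this conservatism is accidental, depends on an unstated correlation, and is paid for in power.

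**The study is exploratory.** There is no power calculation, tolerability comes first among the primary endpoints, and the products are cosmetics without an IND. However, the remark about feasibility and exploratory studies in the Data Analysis section is form guidance. The protocol never adopts that label, and it states an efficacy hypothesis with a significance level. The objection does not remove the fault, though it does show one legitimate way to close it.

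**The test count is a construction.** This stands. The plan says outcomes will be compared; it does not say that each measure is tested at each visit. That is why the range runs from 6 to 40. A still higher count, with right-hand tests at weeks 26 and 52, might be read into Figure 1, but the long-term follow-up text covers face and decolletage only.

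**Conclusion.** The concern holds as two faults. The test does not fit the design, and that follows from the text alone. The size of the harm rests on assumed correlations: power of about 68%, 51% or 22% in place of 80% at r = 0.3, 0.5 or 0.7. The absence of a deciding measure, visit or contrast, and of any failure criterion or multiplicity rule, is also plain from the text.

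Inflation under the written plan is not established. Its family-wise error could lie well above or well below 5%, depending on r and on the number of tests. The practical link between the faults is that correcting the test alone would expose the full multiplicity, so both belong in one amendment.

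A reader might also infer that no result could count against the hypothesis. That goes too far: significant worsening from baseline, or a significant result favouring the competitor, would do so. The supportable statement is that no failure criterion is written down.

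This should be changed, but it does not invalidate the data to be collected.

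**What to change.** Amend the Endpoints and Data Analysis sections as follows.

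- Replace the independent tests with paired t tests on within-subject differences (Wilcoxon signed-rank if non-normal; McNemar for paired categorical data). For the hands, compare change from baseline between the HPE hand and the competitor hand.
- Define each imaging measure as one value per subject and site.
- Make week 12 the deciding visit. It is the last visit due for all 80 subjects and both hands.
- Either name one deciding measure per contrast, or apply Holm over the five named measures within each contrast, at two-sided 0.05 each (0.025 each if 5% overall is wanted).
- Report all other visits, sites and measures with 95% confidence intervals and no significance claims.
- If efficacy is meant to be exploratory, say so, drop the confirmatory claim, and still use paired tests.

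**Cost.** A text amendment, with no new visits or data. Under Holm, the detectable effect at 80 pairs and 80% power rises from 0.32 to 0.39 SD of the difference at the strictest step, or 0.42 if alpha is split. Naming one measure per contrast at 0.05 keeps it at 0.32. Results at weeks 6, 26 and 52 become supportive.

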Subjects will undergo clinical evaluations as outlined below on day 0, week 6 and week 12, which will include a subject questionnaire rating subjective parameters (Global Aesthetic Improvement Scale and Cosmetic Improvement Scale) and high resolution, standardized imaging (Canfield VISIA CR Gen 5 with 3DPrimos) to evaluate targeted fluorescence imaging of protoporphyrin-IX and coproporphyrin-III for measuring microbial activity, standard white light and polarized imaging for textural and topographical information, RBX® Red/Brown processing for measuring pigmentation, and 3D imaging with Primos for roughness and volumetric measurements. All subjects will have skin microbiome analysis performed from the face at baseline and week 12 unless they did not meet criteria (i.e., washed face 3-hours prior to clinical visit, which would shift the skin microbiome; or prior allergy to adhesives) or unless they decline. Skin microbiome analysis would be performed by skin swab and tape-stripping. Subjects (up to n=80) who are interested in being involved for a longer duration in the study will be followed to 26-week and 52-week time points for long-term analysis of topical HPE on facial and decolletage skin per subject preference. Subject renumeration will be provided for skin biopsies, and follow-up 26- and 52-week visits.

At the end of the study participants will be asked if they would like to participate in a video interview using an interview guide. Participants that don't continue use of the products after 12 weeks, will be given the option to return to the clinic for photos at 6 months and 12 months. These participants will be given another bottle of the study product.

We will use a zoom type platform and capture study participants thoughts and attitudes towards overall skincare routines and HPE (plated) TM SkinScience product. Each selected patient will be recorded in a 30-minute interview. The interviews will be transcribed, edited for patient testimonials (2–3-minute videos) and used in marketing and patient education materials.

Amendment 2X concentration study:

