We will enroll an additional 50 patients as part of a substudy. We aim for 30-40% people of color. We will partner with DMC BIPOC entrepreneur (MotivateMe) for community outreach and engagement. They will have the same study visits and surveys at baseline, 6 weeks, and 12 weeks. Biopsies will be optional and can be done on the left forearm and/or upper inner arm at baseline and at 12 weeks. At 12 weeks the biopsy

will be on the right arm in a similar area as the left. Participants will receive \$250 for each biopsy. All subjects will have microbiome (swab and tape) at baseline and 12 weeks. All subjects will have standard face/neck photography and 3D imaging at all three visits. Subjects in this 2X study will be reimbursed \$50 for the first two study visits. They will receive \$100 for the 12 week visits. Same inclusion and exclusion criteria. We will ask males to be shaved for their photos.

Participants will be given the option to return to the clinic for photos at 6 months and 12 months. These participants will be given another bottle of the study product.

We will pursue collaboration with MotivateMe, LLC local Latinx/Hispanic entrepreneur for skin of color patient recruitment. This is a collaborative effort with Center for Health Equity and Community Engagement Research

We have been approached by the Rochester Post Bulletin for an article regarding our clinical study and skin of color patient recruitment. This has been vetted by Mayo Pubic Affairs team, but there is concern that IRB may consider this article as a recruitment tool. We will also use social media (see social media plan attachment)

Subject Information

Target accrual is the proposed total number of subjects to be included in this study at Mayo Clinic. A "Subject" may include medical records, images, or specimens generated at Mayo Clinic and/or received from external sources.

Target accrual: 80 + 50 from substudy = 130

Subject population (children, adults, groups):

Adults age 40 to 85 years with moderate photoaging.

Inclusion Criteria:

- 1. Adult males and females ages 40 to 85 years

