 - i) 1 Exception: Very much improved and optimal cosmetic result for the subject
 - ii) 2 Moderate: Much improved and marked improvement in condition, but not optimal for subject; touch-up would slightly improve the result
 - iii) 3 Slight: Improved with obvious improvement but touch-up or retreatment indicated
 - iv) 4 No change: Appearance essentially the same as original condition
 - v) 5 Worse: Appearance worse than original condition
 - b) Cosmetic Improvement Scale [8]: The following parameters will be scored as a percentage of total responses from participants.
 - i. Percentage of subjects satisfied or very satisfied with the treatment
 - ii. Percentage of subjects who would recommend the treatment to a friend
 - iii. Percentage of subjects reporting high likelihood of continuing treatment
 - iv. Percentage of subjects reporting treatment positively or negatively affected self-esteem
 - v. Percentage of subjects reporting no, minimal, moderate, or significant improvement in fine lines and wrinkles, skin tone, skin smoothness and/or puffiness

Data collection

Data collection, processing, transmission, and storage will follow Mayo Clinic Data Protection Standards. Redcap, a Mayo-endorsed, password protected HIPAA-compliant system, will be used as the electronic data collection and management system. It allows data tracking and downloads to statistical analysis packages. Participant informed consents will be tracked using Ptrax. Participant questionnaires will be collected using REDCap.

Canfield VISIA CR Gen 5 with 3DPrimos will be used to evaluate qualitatively and quantitatively skin profile changes. If Canfield is processing any data on behalf of Sponsor, Canfield shall do so in strict accordance and compliance with applicable laws, rules, and regulations, including to the extent applicable, the Health Insurance Portability and Accountability Act of 1996 and the Regulation (EU) 2016/679 of the European Parliament and the Council of 27 April 2016 on the protection of natural persons with regard to the processing of personal data and on the free movement of such data (GDPR), and with Sponsor's instructions, and it shall not utilize said data for any other purpose whatsoever without obtaining data subject's consent first.

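### Photoaging change at weeks 26 and 52 is primary alongside weeks 6 and 12, but those visits are elective and have no analysis set or product-use rule, so the result is open to selection bias of unknown sign and size

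*Combined protocol and SAP*

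**What the plan says.** Under Endpoints, Primary, the photoaging endpoint is "Change in photoaging scores from Baseline at 6,12, 26- and 52-weeks", measured with the VISIA-CR system. Nothing in the protocol ranks the four time points.

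Weeks 6 and 12 (Visits 1 and 2) are scheduled for all subjects. For the later visits, Study Design and Methods says that up to 80 subjects "who are interested in being involved for a longer duration in the study will be followed to 26-week and 52-week time points", according to their preference. The footnote to Table 1 likewise offers these visits to everyone but leaves them optional. They are paid: "Subject renumeration will be provided for skin biopsies, and follow-up 26- and 52-week visits".

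The next paragraph of the Methods adds: "Participants that don't continue use of the products after 12 weeks, will be given the option to return to the clinic for photos" at 6 and 12 months, which Table 1 equates with weeks 26 and 52. It continues: "These participants will be given another bottle of the study product".

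The Data Analysis Plan specifies independent two-group t tests for continuous data at the 0.05 level and says: "Treatment effects on outcomes will be compared between baseline versus HPE and HPE versus market competitor group". It does not say who enters the HPE group at a given visit, how product use is judged, or what happens to subjects who do not attend.

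The protocol is inconsistent on product use after week 12:

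- The baseline Treatment section has HPE applied throughout the study.
- The Visit 2 section has it continuing in 20 subjects, yet gives every subject a kit containing HPE.
- The Visit 2 section calls that kit the second one, although the second kit is issued at Visit 1.
- The heading for Visits 3 and 4 allows a cohort of up to 80.

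**The concern.** Two of the four primary time points would be estimated in a group that chose itself. The protocol treats willingness to carry on as something that differs between subjects, since one secondary item is "Percentage of subjects reporting high likelihood of continuing treatment". If those who see more improvement are likelier to return, the mean change among returners overstates the change in all 80. If disappointed subjects return more often, for payment or for another bottle, it understates it.

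The plan also lets two analysts choose different week-52 populations, such as all returners or continuing users only, and both would be following it. Whichever they chose would carry the label primary.

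Weeks 6 and 12 do not share the elective-attendance problem, although ordinary dropout can occur there. The lack of a concurrent comparator on the face applies at every visit and is a separate matter.

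**Working it through.** **No figure to reproduce.** The protocol gives no power calculation, effect size, SD, dropout or uptake for weeks 26 and 52. The only document figure used below is the 80 main-study subjects. Everything else is an assumption, and the result is an illustration.

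**Bias in the mean.** Assumed inputs:

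- f: the fraction of the 80 who return.
- c: the correlation of whatever drives return with week-12 change.
- r: the correlation of week-12 change with later change.

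Assume joint normality, that the driver is linked to later change only through week-12 change, and that those highest on the driver return. Then, in SD of later change,

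bias = c × r × φ(k)/f,

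where k is the normal cut-point that leaves a fraction f above it.

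| Returning | f | φ(k)/f | Weak: c=0.25, r=0.3 (c×r=0.075) | Middle: c=0.5, r=0.6 (c×r=0.30) |
|---|---|---|---|---|
| 80 | 1 | 0 | 0 | 0 |
| 60 | 0.75 | 0.318/0.75 = 0.424 | 0.03 | 0.13 |
| 40 | 0.50 | 0.399/0.50 = 0.798 | 0.06 | 0.24 |
| 20 | 0.25 | 0.318/0.25 = 1.271 | 0.10 | 0.38 |

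Simulation with 80 subjects agrees: 0.126, 0.237 and 0.376 in the middle case, and 0.031, 0.059 and 0.093 in the weak case. If return favours poorer responders, every sign reverses.

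**Effect on the planned test.** Suppose the true later change is zero. The planned test treats baseline and later values as independent groups, so its error rate also depends on ρ, the correlation between a subject's baseline and later scores. The documents do not give ρ. Take the middle case with 40 returning, and scores of equal variance and SD 1:

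- SD of change = √(2(1−ρ)): 1.183 at ρ=0.3 and 0.632 at ρ=0.8.
- Bias in score units = 0.239 × that SD: 0.283 and 0.151.
- Standard error used by the test = √(2/40) = 0.224. Bias divided by it: 1.26 and 0.68.
- True spread of the difference relative to that standard error = √(1−ρ): 0.837 and 0.447.
- Chance of a significant result: P(Z > (1.96−1.26)/0.837 = 0.83), about 20%; and P(Z > (1.96−0.68)/0.447 = 2.87), about 0.2%.

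Simulated rejection rates in the middle case, for 60, 40 and 20 returning:

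| ρ | 60 | 40 | 20 |
|---|---|---|---|
| 0.3 | 8.9% | 19.9% | 25.3% |
| 0.5 | 3.8% | 10.3% | 14.3% |
| 0.7 | 0.6% | 2.3% | 3.9% |
| 0.8 | 0.1% | 0.3% | 1.0% |

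In the weak case every rate is about 3% or less. No single false-positive rate can be quoted. The low rates at high ρ arise because the test ignores the pairing; the bias in the mean remains.

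**Do stoppers' images enter the endpoint?** The Methods offer stoppers photos. The visit lists and Table 1 show VISIA-CR imaging and photography as separate items, and the 2X substudy text separates them too: "All subjects will have standard face/neck photography and 3D imaging at all three visits". Against that, the endpoint section describes VISIA-CR output as photographic. The text does not settle the matter, and it does not say how many will stop, so no figure for mixing is given.

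**The case against.** The strongest reply is that the size is wholly assumed. The documents give no uptake, the visits are paid and offered to all, and the bias vanishes if everyone returns. In the weak case it is at most 0.10 SD. All of that stands, and it is why the claim is one of risk with unknown sign and size.

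Second, a reader might infer that the protocol has no long-term target at all. That goes too far. The Methods describe the later follow-up as serving a long-term analysis of HPE on the face and decolletage, and the baseline Treatment section has HPE used throughout the study. Together these suggest change on product. But this is not written as a rule, and the analysis plan does not carry it into an analysis set.

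Third, a reader might infer that users and stoppers will be pooled. The documents do not show this. Stoppers are offered photos, while the endpoint rests on VISIA-CR. The long-term visits include jar weighing and log review, which fits people using product. Mixing is a point to clarify. It would matter only if stoppers' images feed the endpoint and the target is change on product; if the target is change regardless of use, pooling is legitimate.

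Fourth, the conflicts over 20 subjects and the second kit may be editorial. They need reconciling, but they are not evidence of bias.

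Finally, one could keep weeks 26 and 52 primary and only define the target and analysis set. That would remove the ambiguity, but the primary result would still depend on elective attendance.

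**Conclusion.** The concern holds in limited form. The plan gives elective visits primary status, names no lead time point, and does not say who is analysed at weeks 26 and 52. A result from returners alone may be biased in either direction. In the illustration the bias is about 0.13 to 0.38 SD of change in the middle case and 0.03 to 0.10 SD in the weak case, for 60 down to 20 of 80 returning. These figures rest on assumed correlations and return numbers.

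A reader might infer that the long-term result will be too favourable, or that a particular share of such trials would be falsely positive. Neither follows. The direction depends on who chooses to return. Under the planned test the middle-case rejection rate runs from about 25% to under 1%, according to the baseline-later correlation (0.3 to 0.8) and the number returning. Nor does the point show bias at weeks 6 or 12. The plan should be changed on this point; confidence is medium, because uptake is unknown.

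**What to change.** 1. Name week 12, the last visit scheduled for everyone, as the primary time point for photoaging change, with week 6 supportive.
2. Make weeks 26 and 52 secondary and descriptive. State the target (change on product, or change regardless of use) and the analysis set. Report continuing users and stoppers separately, using the treatment logs and jar weights already reviewed at Visits 3 and 4.
3. Tabulate baseline and week-12 imaging, and the week-12 questionnaire results including the likelihood-of-continuing item, for returners against non-returners.
4. Reconcile Study Design and Methods, the baseline Treatment section, the Visit 2 and Visits 3 and 4 sections and the Table 1 footnote on who continues the product and who attends after week 12. Say whether the photos offered to stoppers include VISIA-CR imaging. This review takes no position on which product-use rule should apply.

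The cost is endpoint and analysis wording plus one table, almost all from data already collected. Subjects who return only for photos would need a short product-use record. The downsides are that the long-term result is no longer a primary result, and that splitting by product use leaves smaller groups at weeks 26 and 52.
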